Appendix A: Health Beliefs for Cardiovascular Disease Survey

	Strongly Disagree			Strongly Agree
1. It is likely that I will suffer from a heart attack or stroke in the future	1	2	3	4
2. My chances of suffering from a heart attack or stroke in the next few years are great	1	2	3	4
3. I feel I will have a heart attack or stroke sometime during my life	1	2	3	4
4. Having a heart attack or stroke is currently a possibility for me	1	2	3	4
5. I am concerned about the likelihood of having a heart attack or stroke in the near future	1	2	3	4
6. having a heart attack or stroke is always fatal	1	2	3	4
7. Having a heart attack or stroke will threaten my relationship with my significant other	1	2	3	4
8. My whole life would change if I had a heart attack or stroke	1	2	3	4
9. Having a heart attack or stroke would have a very bad effect on my sex life	1	2	3	4
10. If I have a heart attack or stroke I will die within 10 years	1	2	3	4
11. Increasing my exercise will decrease my chances of having a heart attack or stroke	1	2	3	4
12. Eating a healthy diet will decrease my chance of having a heart attack or stroke	1	2	3	4
13. Eating a healthy diet and exercising for 30 minutes most days will help to prevent a heart attack or stroke	1	2	3	4
14. When I exercise I am doing something good for myself	1	2	3	4
15. When I eat healthy I am doing something good for myself	1	2	3	4
16. Eating a healthy diet will decrease my chances of dying from cardiovascular disease	1	2	3	4
17. I don't know appropriate exercises to perform to reduce my risk of developing cardiovascular disease	1	2	3	4
18. It is painful for me to walk for more than 5 minutes walking	1	2	3	4
19. I have access to exercise facilities and or equipment	1	2	3	4
20. I have someone who will exercise with me	1	2	3	4

Protocol

21. I don't have time to exercise for 30 minutes a day on most days of the week	1	2	3	4
22. I don't know what is considered a healthy diet that would prevent me from developing cardiovascular disease	1	2	3	4
23. I don't have time to cook meals for myself	1	2	3	4
24. I cannot afford to buy healthy foods	1	2	3	4
25. I have other problems more important than worrying about diet and exercise	1	2	3	4

Appendix B: Adherence to Hypertension and Cholesterol Medication Scales

Adherence for blood pressure medication

In order for blood pressure medication to work, people have to take it according to their doctor's instructions. For one reason or another, people can't or don't always take all of their pills as prescribed. We want to know how often you have missed your blood pressure medication. Please rate your agreement with the following statements.

Over the past 7 days...

1. I took my blood pressure medication as prescribed.	Strongly disagree		Strongly agree				
2. I missed or skipped at least one dose of my blood pressure medication.	Strongly disagree		Strongly agree				
3. I was not able to take all of my blood pressure medication.	Strongly disagree		Strongly agree				

Scoring instructions: nonadherence scale score - calculating the mean of the three extents of nonadherence items. Higher scores indicate greater levels of non-adherence

Reasons for Nonadherence to Blood Pressure Medicines

Situations come up that make it difficult for people to take their blood pressure medications as prescribed by their doctors. Below is a list of those situations. We want to know how much these situations contributed to you missing a dose of your medication. Only one of these situations may apply to you, or many may apply to you.

In the past 7 days, how much did each situation contribute to you missing a dose of your blood pressure medication?

1. I was busy	Not at all		Very much				
2. There was no one to remind me	Not at all		Very much				
3. They caused some side effects	Not at all		Very much				
4. I worried about taking them for the rest of my life	Not at all		Very much				
5. They cost a lot of money	Not at all		Very much				
6. I came home late	Not at all		Very much				
7. I did not have any symptoms of high blood pressure	Not at all		Very much				
8. I was with friends or family members	Not at all		Very much				
9. I was in a public place	Not at all		Very much				

Protocol

10. I was afraid of becoming dependent on them	Not at all		Very much				
11. I was afraid they may affect my sexual performance	Not at all		Very much				
12. The time to take them was between my meals	Not at all		Very much				
13. I felt I did not need them	Not at all		Very much				
14. I was travelling	Not at all		Very much				
15. I was supposed to take them more than once a day	Not at all		Very much				
16. I had other medications to take	Not at all		Very much				
17. They make me want to urinate while away from home	Not at all		Very much				
18. I ran out of medication	Not at all		Very much				
19. I was afraid the medication would interact with other medication I take	Not at all		Very much				
20. My blood pressure was too low	Not at all		Very much				
21. I was feeling too ill to take them	Not at all		Very much				

Scoring instructions: These items are used individually; no total score is computed.

Adherence for cholesterol lowering medication

In order for cholesterol medication to work, people have to take it according to their doctor's instructions. For one reason or another, people can't or don't always take all of their pills as prescribed. We want to know how often you have missed your cholesterol medication. Please rate your agreement with the following statements.

Over the past 7 days...

4. I took my cholesterol medications as prescribed.	Strongly disagree		Strongly agree				
5. I missed or skipped at least one dose of my cholesterol medications.	Strongly disagree		Strongly agree				
6. I was not able to take all of my cholesterol medication.	Strongly disagree		Strongly agree				

Scoring instructions: nonadherence scale score - calculating the mean of the three extents of nonadherence items. Higher scores indicate greater levels of non-adherence

Reasons for Nonadherence to Cholesterol Medicines

Situations come up that make it difficult for people to take their cholesterol lowering medication as prescribed by their doctors. Below is a list of those situations. We want to know how much these situations contributed to you missing a dose of your medication. Only one of these situations may apply to you, or many may apply to you.

In the past 7 days, how much did each situation contribute to you missing a dose of your cholesterol medication?

1. I was busy	Not at all		Very much				
2. I forgot	Not at all		Very much				
3. The medication caused some side effects.	Not at all		Very much				
4. I worried about taking them for the rest of my life	Not at all		Very much				
5. They cost a lot of money	Not at all		Very much				
6. I came home late	Not at all		Very much				
7. I did not have any symptoms of high cholesterol	Not at all		Very much				
8. I was with friends or family members	Not at all		Very much				
9. I was in a public place	Not at all		Very much				

Protocol

10. I was afraid of becoming dependent on them	Not at all		Very much				
11. I was afraid they may affect my liver.	Not at all		Very much				
12. The time to take them was between my meals	Not at all		Very much				
13. I felt I did not need them	Not at all		Very much				
14. I was travelling	Not at all		Very much				
15. I was supposed to take them too many times a day.	Not at all		Very much				
16. I had other medications to take	Not at all		Very much				
17. I was afraid they would cause muscle pain.	Not at all		Very much				
18. I ran out of medication	Not at all		Very much				
19. I was afraid the medication would interact with other medication I take	Not at all		Very much				
20. My cholesterol was too low.	Not at all		Very much				
21. I was feeling too ill to take them.	Not at all		Very much				

Scoring instructions: These items are used individually; no total score is computed.

Appendix C: Interview Guides AIM 1

Key Informant Interview Guide for Patients Living with HIV

Introduction

[Remind about Audio Recording and not to use real names]

Thank you for talking with us today. We are interested in learning more about your thoughts and beliefs about cardiovascular or heart disease. I am going to ask you some questions about these topics to hear about your experiences and perspectives. Please know that there is no right or wrong answer. You will notice that I won't give you a lot of feedback on your responses because I don't want to influence your answers. You may also notice that I will jot things down on paper while you talk- this is simply a reminder to ask you a follow-up question. Finally, you are under no obligation to talk about anything that you are not comfortable discussing with me. Do you have any questions or concerns before we begin?

Primary Questions

General CVD Perceptions

Let's start by you telling me about what you know about cardiovascular or heart disease.

Prompts: What is heart disease; what causes heart disease; how do you prevent it; how do you treat it if you get it; how do you know if you have it?

Do you think you are at risk for developing heart disease? Why? Prompts: Family history, past or current substance use, obesity, inactivity, diet, medications you take

What do you know about the risk factors for stroke? Are they similar or different from other heart disease risk factors?

When you think about your passing, what do you think you will eventually die from? (e.g., AIDS, heart disease or something else)

Have any of your doctors or nurses ever talked with you about heart disease? If yes, what did they tell you? Have you ever asked your HIV doctor about your risk of developing heart disease? Do you have a separate primary care doctor (from your HIV doctor)? If so, did have they ever talked with you your risk for heart disease?

Have you ever been evaluated for heart disease by a doctor? If so, what did he or she do? Was it your HIV doctor or another doctor? What led to that evaluation (e.g., symptoms (chest pain, swelling, etc...))

What are the medications that are used to prevent heart attacks and strokes?

Do you tend to be more worried about side-effects of medications or are you more worried about what will happen if you don't take the medications?

Tell me about a time when your doctor or nurse has talked with you about your risk for having a heart attack or heart problems? Probes: What prompted that discussion (e.g., did you bring it up, was it part of a research study, did you have abnormal blood pressure or cholesterol?)

Have you been prescribed medications for blood pressure or cholesterol? Do you know what the medication is? How often do you take it? What makes it hard to take it? Easy?

Do you check your blood pressure at home or anywhere outside of a doctor's office? If so, how often do you check it?

What else do you do to help prevent heart problems? Who or what helps you do that?

HIV and CVD

Do you think HIV affects your risk for heart disease? If so, how?

Has anyone in your doctor's office ever talked with you about the relationship between HIV and heart disease? Who? What did they tell you? How did you respond to that conversation? Did it impact how you take care of yourself? How?

What HIV medications are you taking? Have you ever heard that some HIV medications can increase your risk of developing heart disease while others do not impact this risk? Where and from whom?

If you knew that HIV medication increases your heart disease risk, would this impact your behavior (e.g., smoking, diet, exercise, taking medications, seeing/talking with your doctor).

Are you concerned about other medications interacting with your HIV drugs? If a non-HIV doctor prescribes a medication for you, do you always check with your HIV doctor before you agree to take it?

Would you be more likely to take a preventive medication (like aspirin or statins) if your HIV doctor prescribed it compared to a non-HIV provider? Why or why not?

Intervention Tailoring

Tell me about a time you improved your health behavior. Who helped you achieve this improvement? What steps did you take to make the change? How long did it last?

Do you ever track anything at home, like your weight or your mood? What would make it easier for you to do so? What if we gave you a kit to monitor your blood pressure? Do you think you could measure it every day? What would be hard about that? What would make it easier?

Other than your doctor, where do you get information about your health? What sources do you trust the most? What sorts of health messages or education do you prefer? What messages motivate or inspire you to change your health behaviors.

What sort of intervention or program might help you improve heart disease prevention behaviors such as smoking cessation, eating a healthier diet, exercising harder and more often, talking with your doctor about how you can determine your own risk for heart disease and take steps to reduce that risk?

Do you like messages that focus on one health behavior change (such as smoking cessation or improving your diet) or multiple changes?

Do you prefer paper, verbal (conversations), digital (phone, computer) or visual (TV) messages to help you understand health information the best and how to best act on that information to improve your health?

Secondary/Follow-up Questions

Follow-up “Probes” after significant statements are made:

[Earlier/A moment ago/when you first started speaking/when you were talking about x] you said [significant statement].

- Can you tell me more about that?
- Can you tell me more about how that affects [X]
- Can you clarify what you mean by [significant statement]
- Can you give me an example of a time when [significant statement] happened to you

Conclusion

Is there anything else you want us to know about [X]? (YES return to interview; NO proceed)

We want to thank you so much for your participation and remind you that everything we have discussed will remain private. The audio file will be destroyed once this interview is transcribed, and the transcription will not contain your name or any identifying information.

Key Informant Interview Guide for Clinicians

Introduction

[Remind about Audio Recording and not to use real names]

Thank you for talking with us today. We are interested in learning more about your thoughts and beliefs about cardiovascular disease among your HIV+ patients. We are most interested in the patients you see in their routine, outpatient HIV care, not those in the hospital. I am going to ask you some questions about these topics to hear about your experiences and perspectives. Please know that there is no right or wrong answer. You will notice that I won't give you a lot of feedback on your responses because I don't want to influence your answers. You may also notice that I will jot things down on paper while you talk- this is simply a reminder to ask you a follow-up question. Finally, you are under no obligation to talk about anything that you are not comfortable discussing with me. Do you have any questions or concerns before we begin?

Primary Questions for all Clinicians

General CVD Perceptions

- Let's start by you telling me about what you think the biggest health problems are for your HIV+ patients.
- Can you tell me what you know about cardiovascular or heart disease and HIV. Prompts: Are your HIV+ patients at risk for developing heart disease? Why? Prompts: Family history, past or current substance use, obesity, inactivity, diet, medications you take
- When you think about your patients passing away, what do you think you will eventually die from? (e.g., AIDS, heart disease or something else)
- Have you ever talked with your patients about heart disease? If yes, tell me about that/those conversation(s)? Prompts: What prompted that discussion (e.g., did you bring it up, was it part of a research study, did you have abnormal blood pressure or cholesterol?) Did they ask you about their risk of developing heart disease? Did their primary care provider reach out to you?
- What are the medications that are used to prevent heart attacks and strokes?
- What can do you do to help prevent heart problems in your HIV+ patients? Who or what helps you do that?

HIV and CVD

- Do you think HIV affects your patient's risk for heart disease? If so, how?
- Have you ever heard that some HIV medications can increase your patient's risk of developing heart disease while others do not impact this risk? Where and from whom?
- How would knowing they are at increased risk for heart disease affect your patients' health behavior (e.g., smoking, diet, exercise, taking medications, seeing/talking with your doctor).

Prescribing provider/pharmacist ONLY questions

- What helps you think about or better manage CVD in your HIV+ patients?
- Do you believe that your patients appropriately recognize their risk of heart disease? If your high-risk patients recognize their risk, are they then motivated to address risk factors and take preventive actions?
- What is your routine for monitoring cholesterol in your patients?
- How often do you review current or past cholesterol results for your patients? Prompts: every visit?, once yearly?, rarely?
- Blood pressure is typically measured at every clinical visit. Do you ever neglect to review the blood pressure because you are focused on other things? Do you ever notice the blood pressure is high but then decide that it is not a high enough priority to address at that visit?
- How comfortable are you with current guidelines about the definitions and management of high blood pressure?
- How comfortable do you feel prescribing hypertension and cholesterol medications and managing their side effects?
- How often do you prescribe home blood pressure monitoring? How do you follow up on adherence to these medications or monitoring? Prompts: Have your nurse call; patient calls in with numbers; check in with patient via email or EMR reminders.
- Do you talk with your patients about how HIV medications affect heart disease risk? If so, tell me about those conversations.
- Do you believe drug-drug interactions is a significant barrier to prescribing preventive medications like statins?
 - **HIV specialty providers:** If a non-HIV doctor prescribes a medication for your patients, do you know about it? How frequently do you encounter dangerous drug-drug interactions that result from others being unfamiliar with ART?
 - **PCPs (i.e. non-HIV provider):** How knowledgeable are you about ART drug interactions? Do you avoid certain statin medications in all HIV patients for fear of drug interactions or do you check for specific interactions based on the patient's ART?
- Do you think your patients would be more likely to take a preventive medication (like aspirin or statins) if your HIV doctor prescribed it compared to a non-HIV provider? Why or why not?
- What types of patients do you refer to a specialist for cardiovascular disease prevention? Prompts: very high LDL or triglycerides (do you have a threshold)? Difficult to control hypertension (do you have a threshold—i.e. not controlled on 3 meds? 5 meds?), + family history?, patient preference/request?
- How comfortable are you ordering cardiovascular testing (i.e. stress tests, echocardiograms, holter/event monitors, coronary calcium scans)?

Nurse and Medical Assistant ONLY questions

- Can you tell me when in the patient visit your patients' blood pressure is assessed? What are the steps involved in measuring it? Is it logically difficult for the patient to rest quietly for a time before it is taken? What makes this hard?
- How often do you reconcile your patients' medications? Do they ever have questions about their blood pressure and cholesterol medications? What sorts of questions do they ask? How do you address the questions?
- Do you assess medication adherence? For which medications? Do you provide feedback to the patient based on the medication adherence levels? What do you do if they are non-adherent? If they are non-adherent to any of their medications do you follow up with them after their visit to see if its changed?

Intervention Feasibly and Usability

Finally, we are interested in designing a new initiative, with a new nurse coordinator, to help your patients reduce their risk of heart disease. However, we know in this and many clinics, there are cultural and systemic issues that can make a new clinic initiative more or less successful. We'd like to get your opinion on these issues and as a reminder, all information you provide will be confidential and aggregated across three clinics.

System

- Tell me about your clinic's culture. What aspects of it help you do your job well and what aspects can make it harder for you? What are the strengths of your clinic?
- Does your clinic have a hierarchy? If so, can you tell me how that affects how decisions are made in your clinic?
- What the priorities of your clinic? Have they change over time?
- Tell me about a clinic initiative that was recently developed to help your patients improve their health behavior. What steps were taken to help make the change? Who initiated the change and how did having that person champion it affect the initiative? How long did it last? What was the outcome (did it work)?

Training

- What sort of education or training do you prefer for new initiatives? Do you prefer paper, verbal (conversations), digital (phone, computer) or visual (TV) training? Individual or Group? Does continuing education credit entice you to complete new trainings? Would you be interested in helping to develop a new training for your clinic on reducing heart disease in your patients?

Design Considerations/Representations

- When you have a patient concern, for example an elevated temperature or a high blood pressure, how does that information get turned into action in this clinic? Can you walk me through the various steps? [consider drawing this out on white board]. How do you involve non-HIV clinicians, for example your patient's primary care provider, in this communication cycle?
- How often do you personally communicate with your patients outside of the clinic setting? How does this communication happen (e.g., phone, EMR, via your nurse). Does the patient usually initiate this contact or do you?

Secondary/Follow-up Questions

Follow-up "Probes" after significant statements are made:

[Earlier/A moment ago/when you first started speaking/when you were talking about x] you said [significant statement].

- Can you tell me more about that?
- Can you tell me more about how that affects [X]
- Can you clarify what you mean by [significant statement]
- Can you give me an example of a time when [significant statement] happened to you

Conclusion

Is there anything else you want us to know about [X]? (YES return to interview; NO proceed)

We want to thank you so much for your participation and remind you that everything we have discussed will remain private. The audio file will be destroyed once this interview is transcribed, and the transcription will not contain your name or any identifying information.

COVID AIM: Key Informant Interview Guide for Patients Living with HIV

Introduction

[Remind about Audio Recording and not to use real names]

Thank you for talking with us today. We are interested in learning more about your thoughts and beliefs about how the coronavirus pandemic (or COVID-19) has impacted your cardiovascular health. I am going to ask you some questions about these topics to hear about your experiences and perspectives. Please know that there is no right or wrong answer. You will notice that I won't give you a lot of feedback on your responses because I don't want to influence your answers. You may also notice that I will jot things down on paper while you talk- this is simply a reminder to ask you a follow-up question. Finally, you are under no obligation to talk about anything that you are not comfortable discussing with me. Do you have any questions or concerns before we begin?

Today's date is: _____ and I am interviewing participant [use study ID]

Primary Questions

General COVID-19 Perceptions

- Let's start by you telling me about what you know about the novel coronavirus.
Prompts: What is it; how do you prevent it; how do you treat it if you get it; how do you know if you have it?
- Do you think you are at risk for becoming infected with coronavirus? Why? **Prompts:** Living situation, work, health care appointments, lack of social/material support?
- Have any of your doctors or nurses ever talked with you about coronavirus? If yes, what did they tell you? Have you ever asked a doctor or nurse about how your HIV may impact your likelihood of becoming sick with coronavirus? What about your other risk factors such as heart disease or high blood pressure?
- Have you ever been evaluated for coronavirus by a health care provider? If so, what did he or she do? Was it your HIV doctor or another doctor? What led to that evaluation (e.g., symptoms (chest pain, fever, etc...))

Isolation

- Tell me about your social interactions since word of coronavirus virus spread in March 2020. **Prompts:** How often do you go outside of your house? Where do you go? How do you get there (e.g., walking, driving, public transportation, bicycle?)
- Has this behavior changed over time (or X months since March 2020)? Why or Why not?

- Who do you talk to regularly on the phone or via computer? How has that changed over time? Who do you feel close to today?
 - Tell me about times when you have felt supported over the past X months?
 - Tell me about times when you have felt alone or isolated? How has that affected your mood? Your health? Your motivation to take care of your health?

COVID and Self-Management

Let's talk a bit more about how any changes you have made to your behavior in response to COVID pandemic may have influenced your health.

- What medications do you take for HIV? What about your heart health?
- How has coronavirus affected your ability to take your medications? **Prompts:** Your schedule is different; motivation changed/diminished; unable to get refills/see your health care provider? You can't travel to get your medications?
- What else do you do to help manage your health? Physical activity, support groups, diet control, regularly clinic appointments, volunteer, read, take daily blood pressure measurements, etc?
 - How has this been impacted by the coronavirus?
- Do you think the spread of coronavirus will impact your ability to take care of your HIV and heart disease over the long-term? How or why not?
- Do you think it will impact your ability or willingness to visit your health care team?
- What are your experiences with telehealth or talking to health care team over the phone or computer? **Prompts:** How comfortable are you? Does it change your relationship with the team?
- What about doing more research visits on the computer or over the phone. Would you be willing to do that? What challenges do you think you might encounter if you did more research visits over the phone or computer? What benefits do you think might occur with more virtual research visits?
- If we were to change EXTRA-CVD to include more virtual visits/calls, what should we keep in mind? **Prompts:** Internet access? Ability to navigate platforms? Should we have an orientation visit first to make sure you understand the technology?
- How about the social support you receive from the research team. How could that be effected by fewer in person visits?
- Do you think more virtual visits would impact your willingness to participate in EXTRA-CVD and other research studies? If so, how could we offset that?

Secondary/Follow-up Questions

Follow-up "Probes" after significant statements are made:

Protocol

[Earlier/A moment ago/when you first started speaking/when you were talking about x] you said [significant statement].

- Can you tell me more about that?
- Can you tell me more about how that affects [X]
- Can you clarify what you mean by [significant statement]
- Can you give me an example of a time when [significant statement] happened to you

Conclusion

Is there anything else you want us to know about [X]? (YES return to interview; NO proceed)

We want to thank you so much for your participation and remind you that everything we have discussed will remain private. The audio file will be destroyed once this interview is transcribed, and the transcription will not contain your name or any identifying information.

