10/29/2019	
• Added 2 week window for date of in person visits• Added table of BP and cholesterol diagnosis terms for determining cascade category• Added clarification of how many attempts will be made to reach potentially eligible patients by phone• Added additional language on recruitment strategies

Protocol

	
• Added checklist for observation of study visit to ensure fidelity
9/16/2019	
• Minor changes to statistical analysis in response to NIH review
9/9/2019	
• Updated BP and Cholesterol treatment protocols• Incorporated process oriented design team recommendations about intervention adaptation.• Added additional detail regarding the aim 3 process evaluation, including the assessment of provider trust and communication ties• Added verbal consent script to obtain age, sex, gender identity, and race/ethnicity from persons who are screened but who decline to participate in the study• Added a recruitment letter and MyChart message (Duke only). Added a telephone script for the follow-up screening call.
2/7/2019	
• Added additional detail to design team process (sub-aim 1.1)• Added 3 additional consents forms for the design team process
○ Design team members (focus group and survey)○ PLHIV pilot participants (focus groups/pilot intervention)○ Feasibility testing among health workers (interview)
10/29/2018	
• Added clinic variables checklist (p. 18 and Appendix D)• Minor change to wording of inclusion criteria #5 and exclusion criteria #1 related to a simplification of the definition of hyperlipidemia• Minor change to cholesterol treatment algorithm (p. 22) clarifying how the prevention nurse will determine non-HDL goal for the purposes of treatment recommendations.• Added scripts for Aim 1 phone consent for (a) healthcare providers and (b) PLHIV (Duke site)• Added recruitment letter for Aim 1 (Duke site)• Added clinicaltrials.gov registration number
8/6/2018	
• Added adherence surveys for PLHIV focus group and clinical trial participants

Protocol

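### Appendix B averages one adherence item with two non-adherence items and states no reversal, so the score as written does not measure what it is said to measure

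*Combined protocol and SAP*

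**What the plan says.** Appendix B (Adherence to Hypertension and Cholesterol Medication Scales) asks about the past 7 days. For blood pressure, the three statements rated for agreement are "I took my blood pressure medication as prescribed", "I missed or skipped at least one dose of my blood pressure medication" and "I was not able to take all of my blood pressure medication". The cholesterol scale has the same structure, numbered 4 to 6, and opens with "I took my cholesterol medications as prescribed". All items share one pair of anchors, from strong disagreement to strong agreement.

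The scoring box is the same under both scales. It gives the calculation and fixes the direction: "nonadherence scale score - calculating the mean of the three extents of nonadherence items. Higher scores indicate greater levels of non-adherence". It does not mention reversing any item, and no other section available for review does so.

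The scales are placed explicitly in Aim 1 Procedures, as part of the self-reported survey for participants living with HIV. The Aim 1 outcomes paragraph says that quantitative data will be summarised to describe the sample. The modification log entry of 8/6/2018 reads "Added adherence surveys for PLHIV focus group and clinical trial participants". The Aim 2 list of assessments for both arms does not name the adherence scales, and Statistical Considerations does not use the score as an outcome, covariate or subgroup.

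**The concern.** Agreement with the second and third items means more non-adherence. Agreement with the first means less. A plain mean of the three therefore has one component pulling against the other two, yet the box says that a high score means non-adherence.

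An analyst who programs the rule as printed gets a number that does not carry the stated meaning. A participant who reports perfect adherence does not get the lowest score, and some pairs of participants come out in the wrong order. At stake is the description of adherence in the Aim 1 sample, and any later use of the score if it is collected in the trials.

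**Working it through.** **Inputs.** From Appendix B: three items per scale, one worded as adherence and two as non-adherence; common anchors; the score is the mean; high means non-adherent. The plan states no numerical value for the score, so there is no figure to reproduce. The number of response points and their codes cannot be read in the available text. I assume 1 to K with K = 5, and show K = 4 and K = 7 as the range.

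**Formulas.** Let x1 be the adherence item and x2, x3 the non-adherence items.

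- As written: W = (x1 + x2 + x3)/3
- With the first item reversed: R = ((K + 1 − x1) + x2 + x3)/3
- Difference: W − R = (2·x1 − (K + 1))/3

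At K = 5 the difference is (2·x1 − 6)/3. It is +1.33 when x1 = 5, zero when x1 = 3, and −1.33 when x1 = 1. The rule as written overstates non-adherence for those who most strongly report taking the drug as prescribed, and understates it for those who most strongly deny it.

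**Consistent responders at the two ends, K = 5.**

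- Fully adherent (5,1,1): W = 7/3 = 2.33; R = (1 + 1 + 1)/3 = 1.00
- Fully non-adherent (1,5,5): W = 11/3 = 3.67; R = (5 + 5 + 5)/3 = 5.00
- Span: 3.67 − 2.33 = 1.33 as written, against 5 − 1 = 4.00 with reversal; 1.33/4.00 = one third

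**Other numbers of response points.** In general W runs from (K + 2)/3 to (2K + 1)/3, a span of (K − 1)/3 against K − 1.

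| K | W, fully adherent | W, fully non-adherent | Span as written | Span with reversal | Fraction |
|---|---|---|---|---|---|
| 4 | 2.00 | 3.00 | 1.00 | 3.00 | 1/3 |
| 5 | 2.33 | 3.67 | 1.33 | 4.00 | 1/3 |
| 7 | 3.00 | 5.00 | 2.00 | 6.00 | 1/3 |

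**Ordering among consistent responders.** If someone answers K + 1 − t on the first item and t on the other two, then W = (K + 1 + t)/3. This rises with t, so their order is kept and their scores are only compressed.

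**Ordering otherwise, K = 5.**

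- (5,2,2): W = 9/3 = 3.00; R = (1 + 2 + 2)/3 = 1.67
- (2,2,2): W = 6/3 = 2.00; R = (4 + 2 + 2)/3 = 2.67

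The two answer the non-adherence items identically. The first strongly agrees that the drug was taken as prescribed, yet is scored as the more non-adherent by a full point. Reversal puts them in the expected order.

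**Limit of the one-third figure.** Contradictory patterns still reach the ends: (1,1,1) gives W = 1 and (5,5,5) gives W = 5. The one third describes people who answer coherently, not the arithmetic range of the mean.

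**The case against.** The strongest reply is that the box calls all three items non-adherence items and fixes the direction of the score, which implies that the first item is aligned before averaging. The study database may already do this. That is possible, and it means nobody can say from the documents that any collected score is wrong. It does not rescue the text: the first item as printed is not a non-adherence item, and the whole meaning of the score rests on a step that is not written down.

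The second reply is that little depends on the score. This stands. Several stronger readings are tempting, and the documents do not support them:

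- **That the wrong people would be classed as non-adherent.** No cut-off or classification is given. What can be said is that ranking can change.
- **That a treatment comparison loses power.** No between-arm or over-time analysis of this score is specified, and the mediation analyses described elsewhere use intervention dose and trust and communication ties. A figure for lost power would also need inter-item correlations that the documents do not give. For perfectly consistent responders the compression is linear and costs no standardised effect.
- **That the scale shrinks for everyone.** The compression to one third applies to coherent answers only.
- **That the main pathway of the intervention is mismeasured.** Adherence support shares a component with nurse-managed medication protocols, and the conceptual framework names lifestyle change and medication adherence together. Nothing singles this score out.
- **That the trials certainly use it.** The log entry shows an intention to survey trial participants, but no section gives a visit schedule or analysis for these scales.

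**Conclusion.** The point holds as a wrong scoring rule with limited reach. Taken literally, the rule in both boxes gives consistent responders one third of the intended span (2.33 to 3.67 instead of 1 to 5 under assumed 1-5 coding) and can reverse the order of people whose answers do not mirror each other. The fraction does not depend on the number of response points; the individual scores do.

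The consequence is confined to this survey measure. Systolic BP, non-HDL cholesterol, power and sample size are untouched. Whether any existing score is affected is unknown until the scoring code is looked at. The correction is worth making because it is nearly free and because the printed rule contradicts its own stated direction.

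**What to change.** In both Appendix B scoring boxes, state that item 1 (blood pressure) or item 4 (cholesterol) is reverse-coded before the mean is taken, as the scale maximum plus the scale minimum, minus the response. On a 1-5 coding that is 6 minus the response. Print the response codes and the resulting range beside the rule.

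Then check how scores already computed, including those from Aim 1, were derived. If the reversal was applied, the new sentence simply documents it. If not, rescore from the item responses.

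The cost is one sentence in each box and, if needed, one line of code. No new data are required, provided the item-level responses were kept, which the documents do not state for this scale.
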